
Study Assessments (see Schedule in Appendix 4):
	
Part A: Patients will be screened within 28 days of dosing and will return for an end-of-study assessment 84 days after receiving their final dose of study drug. During the study, patients will return at specified times on an outpatient basis for assessment of vital signs, physical examination, assessment of AEs, assessment of concomitant medication use, assessment of clinical benefit, and provision of blood samples for PK and PD, and other clinical laboratory tests.
 
Note: Patients who are currently enrolled in this PRN1008-005 study (Part A) and are in the 12-week active treatment period with PRN1008 are eligible to continue treatment at their current dose up to a total of 24 weeks active treatment, as a Part B patient, upon review and signature of the Part B EC-approved Patient Informed Consent Form. Patients that completed Part A of the trial are also eligible to be screened as a Part B patient, upon review and signature of the Part B EC-approved Patient Informed Consent Form.
 
Part B: Patients will be screened within 28 days of dosing and will return for an end-of-treatment assessment on Day 169 after receiving their final dose of study drug on the morning of Day 169. They will return for follow up 28 days later for a final, follow up visit. During the study, patients will return at specified times on an outpatient basis for assessment of vital signs, physical examination, assessment of AEs, assessment of concomitant medication use, assessment of clinical benefit, and provision of blood samples for PK and PD, and other clinical laboratory tests.
 
Clinical Assessments Part A and B:
 
 • Medical history, including evaluation of any on-study AEs and periodic vital signs (body temperature, heart rate, respiratory rate, blood pressure), concomitant medication use • At screening only: height and weight, full physical examination, and 12-lead electrocardiogram (ECG) (an extra ECG may be taken at additional visits, if indicated) • Disease activity scores: PDAI, ABSIS (Appendix 5) • Standardized photography of the affected area (Optional) • Quality of Life Scores: ABQOL, TABQOL (Appendix 5) • SNAQ appetite questionnaire (Appendix 6)

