3.4.3 Pre-treatment vs. treatment emergent vs. post last dose adverse events

Pre-treatment events are the events that started prior to the first study drug dosing.

Treatment emergent adverse events (TEAEs) are the events started on or after the first study drug.

Post last dose adverse events are the events that started after the last date of study drug dosing.

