Adverse events are attributed to the dose level where the AE start date is on or after the start date of the dose level, but before the next dose level, if applicable.

Pre-treatment adverse events are the events that started prior to the first dose.

Treatment emergent adverse events are the events started on or after the first dose of study drug and prior to the date of last dose of study drug.

Post last dose adverse events are the events started after the last dose of study drug.

* Patient is counted for each reported Action taken, therefore patient may be counted more than once.

Program: <program name (date, time)>, Path: <path>

Programming note for all AE tables with “Post Last Dose” column: N for Post Last dose column is the number of patients reported a Date of Last Dose.

Table B.14.3.1.2 Treatment Emergent Adverse Events by SOC and PT (Safety Population)

System Organ Class (SOC) Preferred Term (PT)	400 mg QD (N = n)		400 mg BID (N = n)		600 mg BID (N = n)		Post Last Dose (N = n)		Overall (N = n)	
	n (%)	[E]	n (%)	[E]	n (%)	[E]	n (%)	[E]	n (%)	[E]
Patients with at least one TEAE	x (x.x)	x	x (x.x)	x	x (x.x)	x	x (x.x)	x	x (x.x)	x
SOC1	x (x.x)	x	x (x.x)	x	x (x.x)	x	x (x.x)	x	x (x.x)	x
PT1.1	x (x.x)	x	x (x.x)	x	x (x.x)	x	x (x.x)	x	x (x.x)	x
PT1.2	x (x.x)	x	x (x.x)	x	x (x.x)	x	x (x.x)	x	x (x.x)	x
PT1.3	x (x.x)	x	x (x.x)	x	x (x.x)	x	x (x.x)	x	x (x.x)	x
SOC2	x (x.x)	x	x (x.x)	x	x (x.x)	x	x (x.x)	x	x (x.x)	x
PT2.1	x (x.x)	x	x (x.x)	x	x (x.x)	x	x (x.x)	x	x (x.x)	x
PT2.2	x (x.x)	x	x (x.x)	x	x (x.x)	x	x (x.x)	x	x (x.x)	x
PT2.3	x (x.x)	x	x (x.x)	x	x (x.x)	x	x (x.x)	x	x (x.x)	x
...etc...										

Patients are classified into different dose levels according to the dose they received at the start of AE.

Percentages are based on the number of patients in each dose group and overall.

Adverse Events were coded using MedDRA, Version 18.0.

Adverse events where PT='Pemphigus' are excluded from this table.

Adverse events are attributed to the dose level where the AE start date is on or after the start date of the dose level, but before the next dose level, if applicable.

Treatment emergent adverse events are the events started on or after the first dose of study drug and prior to the date of last dose of study drug.

Adverse events are sorted by overall descending frequency of SOC and within each SOC, by overall descending frequency of PT.

Program: <program name (date, time)>, Path: <path>

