Table B.14.3.1.3 Related Treatment Emergent Adverse Events by SOC and PT (Safety Population)

System Organ Class (SOC) Preferred Term (PT)	400 mg QD (N = n)		400 mg BID (N = n)		600 mg BID (N = n)		Post Last Dose (N = n)		Overall (N = n)	
	n (%)	[E]	n (%)	[E]	n (%)	[E]	n (%)	[E]	n (%)	[E]
Patients with at least one related TEAE	x (x.x)	x	x (x.x)	x	x (x.x)	x	x (x.x)	x	x (x.x)	x
SOC1	x (x.x)	x	x (x.x)	x	x (x.x)	x	x (x.x)	x	x (x.x)	x
PT1.1	x (x.x)	x	x (x.x)	x	x (x.x)	x	x (x.x)	x	x (x.x)	x
PT1.2	x (x.x)	x	x (x.x)	x	x (x.x)	x	x (x.x)	x	x (x.x)	x
PT1.3	x (x.x)	x	x (x.x)	x	x (x.x)	x	x (x.x)	x	x (x.x)	x
SOC2	x (x.x)	x	x (x.x)	x	x (x.x)	x	x (x.x)	x	x (x.x)	x
PT2.1	x (x.x)	x	x (x.x)	x	x (x.x)	x	x (x.x)	x	x (x.x)	x
PT2.2	x (x.x)	x	x (x.x)	x	x (x.x)	x	x (x.x)	x	x (x.x)	x
PT2.3	x (x.x)	x	x (x.x)	x	x (x.x)	x	x (x.x)	x	x (x.x)	x
...etc...										

Patients are classified into different dose levels according to the dose they received at the start of AE.

Percentages are based on the number of patients in each dose group and overall.

Adverse Events were coded using MedDRA, Version 18.0.

Adverse events where PT='Pemphigus' are excluded from this table.

Adverse events are attributed to the dose level where the AE start date is on or after the start date of the dose level, but before the next dose level, if applicable.

Treatment emergent adverse events are the events started on or after the first dose of study drug and prior to the date of last dose of study drug.

Adverse events are sorted by overall descending frequency of SOC and within each SOC, by overall descending frequency of PT.

Program: <program name (date, time)>, Path: <path>

Table B.14.3.1.4 Treatment Emergent Adverse Events by Maximum Intensity, SOC and PT (Safety Population)

System Organ Class (SOC) Preferred Term (PT)	Overall (N = n)									
	Grade 1		Grade 2		Grade 3		Grade 4		Grade 5	
	n (%)	[E]	n (%)	[E]	n (%)	[E]	n (%)	[E]	n (%)	[E]
Patients with at least one TEAE	x (x.x)	x	x (x.x)	x	x (x.x)	x	x (x.x)	x	x (x.x)	x
SOC1	x (x.x)	x	x (x.x)	x	x (x.x)	x	x (x.x)	x	x (x.x)	x
PT1.1	x (x.x)	x	x (x.x)	x	x (x.x)	x	x (x.x)	x	x (x.x)	x
PT1.2	x (x.x)	x	x (x.x)	x	x (x.x)	x	x (x.x)	x	x (x.x)	x
PT1.3	x (x.x)	x	x (x.x)	x	x (x.x)	x	x (x.x)	x	x (x.x)	x
SOC2	x (x.x)	x	x (x.x)	x	x (x.x)	x	x (x.x)	x	x (x.x)	x
PT2.1	x (x.x)	x	x (x.x)	x	x (x.x)	x	x (x.x)	x	x (x.x)	x
PT2.2	x (x.x)	x	x (x.x)	x	x (x.x)	x	x (x.x)	x	x (x.x)	x
PT2.3	x (x.x)	x	x (x.x)	x	x (x.x)	x	x (x.x)	x	x (x.x)	x
...etc...										

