Treatment emergent adverse events are the events started on or after the first dose and prior to the date of last dose of study drug.

If Date >= first dose date, then Study Day = (Date - Date of first dose +1). If Date < first dose date, then Study Day = (Date - Date of first dose).

Program: <program name (date, time)>, Path: <path>

Programming note for all TEAE listings: Display "Post last dose" if AE started after date of last study drug dosing

Same listing shell will be used for the following listing:

Listing B.16.2.7.4 Related Treatment Emergent Adverse Events (Safety Population)

Listing B.16.2.7.5 Serious Adverse Events (Safety Population)

Programming note: The following variables will be added to the “SAE” column for the SAE listing: Start Date (ddMMMyyyy) (Study Day), Stop Date (ddMMMyyyy) (Study Day) or Ongoing, Duration (if not ongoing), SAE Criteria

Listing B.16.2.7.6 Treatment Emergent Adverse Events Leading to Study Drug Discontinuation (Safety Population)

Listing B.16.2.7.7 Serious Treatment Emergent Adverse Events Leading to Study Drug Discontinuation (Safety Population)

Starting Dose	Patient ID	Age/ Gender	PRN Dose Level at AE start	SOC: System Organ Class PT: Preferred Term V: Verbatim	Start Date (ddMMMyyyy) (Study Day) Stop Date (ddMMMyyyy) (Study Day) or Ongoing Duration (if not ongoing)	SAE? (Y/N) If yes: Start Date (ddMMMyyyy) (Study Day) Stop Date (ddMMMyyyy) (Study Day) or Ongoing Duration (if not ongoing)	CTCAE Grade	Relationship to Study Drug	Details
400 mg QD	xxxxxxx	xx/F	400 mg QD	SOC: xxx PT: xxx V: xxx	Start: ddMMMyyyy (Day X) Stop: ddMMMyyyy (Day X) Duration: x days Pattern: xxx	Y Start: ddMMMyyyy (Day X) Stop: ddMMMyyyy (Day X) Duration: x days SAE Criteria: xxx Hospitalization: Initial or Prolongation Admission Date: Discharge Date: Date of Death: Cause of Death: Autopsy performed?: Death certificate completed?:	Grade x	xxxx	Action Taken to study drug: xxx Outcome: xxx Has the Cause of the AE been established: Y - xxx Caused study discontinuation?: N or Y Treated for this AE?: Y or N (AE description)

	
Description of SAE: Did the SAE abate after use of study treatment stopped? Did the SAE reoccur after reintroduction of study treatment? Interruption of study treatment: Date stopped: Date restarted: Type of Sequelae: PI rationale for "Not Related":

--	--

F=Female; M=Male

Adverse Events were coded using MedDRA, Version 18.0.

Serious Adverse events where PT='Pemphigus' are included in this listing.

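### Part B adverse-event footnotes end the TEAE window before the last-dose date, contrary to SAP 3.4.3 and to the tables' own Post Last Dose column

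*SAP*

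**What the plan says.** Part B SAP 3.4.3 gives the definitions in the body of the plan. On treatment emergence: "Treatment emergent adverse events (TEAEs) are the events started on or after the first study drug". On the period after treatment: "Post last dose adverse events are the events that started after the last date of study drug dosing". The first has no end-point, so under 3.4.3 a post-last-dose event is also a TEAE.

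The mock shells in Section 6 say something else. The footnote repeated under all seven tables, B.14.3.1.1 to B.14.3.1.7, defines TEAEs as "the events started on or after the first dose of study drug and prior to the date of last dose of study drug". Listings B.16.2.7.3 and B.16.2.7.7, and the listings built on the first of these, end the window at the same place. Table B.14.3.1.1 adds the two neighbouring categories: "Pre-treatment adverse events are the events that started prior to the first dose" and "Post last dose adverse events are the events started after the last dose of study drug". The programming note for all TEAE listings shows the post-last-dose label "if AE started after date of last study drug dosing".

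The protocol synopsis (Study Assessments, Part B) fixes the timing of the final dose: patients "will return for an end-of-treatment assessment on Day 169 after receiving their final dose of study drug on the morning of Day 169". The Part B schedule places AE review, haematology, coagulation, chemistry, vital signs and an abbreviated physical examination at that visit.

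**The concern.** The incidence of TEAEs is the primary safety outcome (Protocol 11.1.1; Part B SAP 4.1), so the rule that decides which events count should be the same wherever it appears. Here the body of the SAP and the footnotes disagree, and the disagreement falls on one particular day.

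That day is not arbitrary. For a patient who completes treatment it is the day of the end-of-treatment visit, so a new event whose onset is recorded as that visit date carries the excluded date. For a patient who stops early it is the last day on drug, so an event that begins and leads to stopping on the same day is excluded as well. That would include exclusion from the serious-event table (B.14.3.1.6) and the table of events leading to discontinuation (B.14.3.1.7). If the footnotes are programmed, such events drop out of the counts. If 3.4.3 is programmed, every printed AE table misstates its own definition.

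**Working it through.** There is no sample-size or error-rate figure behind this point and so none to reproduce. The check is whether the stated windows cover every onset date.

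Let F be the date of first dose, L the date of last dose and d the onset date.

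- Footnotes, with the date-based post-last-dose rule of 3.4.3 and the listing note: pre-treatment if d < F; TEAE if F ≤ d < L; post last dose if d > L.
- SAP 3.4.3: pre-treatment if d < F; TEAE if d ≥ F; post last dose if d > L (a subset of TEAE).

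Under the footnotes nothing covers d = L. Three cases were worked through, all with F = Day 1. L = 169 is the planned Part B course, L = 40 is an assumed early stop, and L = 1 is a single dosing day.

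| L | Onset day d | Footnotes | SAP 3.4.3 |
|---|---|---|---|
| 169 | 168 | TEAE | TEAE |
| 169 | 169 | none | TEAE |
| 169 | 170 | post last dose | TEAE and post last dose |
| 40 | 39 | TEAE | TEAE |
| 40 | 40 | none | TEAE |
| 40 | 41 | post last dose | TEAE and post last dose |
| 1 | 1 | none | TEAE |
| 1 | 2 | post last dose | TEAE and post last dose |

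Classifying every onset day from −28 to 197 leaves exactly one unclassified day in each case under the footnotes (Day 169, Day 40 and Day 1) and none under 3.4.3. With L = F = 1 the condition 1 ≤ d < 1 cannot be met, so the TEAE window is empty. Such a patient is realistic: a programming note in the Part A shells (Table 14.2.2.5.4.1) deals with a subject who terminated on the first day of treatment.

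The footnote also conflicts with the tables it sits under. Tables B.14.3.1.1 to B.14.3.1.3, B.14.3.1.6 and B.14.3.1.7 have a Post Last Dose column for TEAEs, and B.14.3.1.4 and B.14.3.1.5 are to be repeated for a Post Last Dose group. Section 5.5.1 asks for a listing of post-last-dose TEAEs, planned as Listing B.16.2.7.9. An event with d > L cannot also satisfy d < L, so under the footnote all of these would be empty. Changing the footnote to end on the last-dose date inclusive would cover d = L but leave this second conflict. Adopting 3.4.3 removes both.

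The Part A SAP (Section 9.1) likewise defines a TEAE from first dose onward with no end-point. The Part B footnote is the outlier.

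**The case against.** The strongest reply is that 3.4.3 governs. Section 6 says that the shells set out layout and may be adjusted. Section 5.5.1 assigns a TEAE to the dose level in force at onset, with no cut at the last dose, and the same footnote blocks repeat that rule. On it, an event on the last-dose day belongs in the column of the final dose level. Because the footnote would empty the Post Last Dose column, the tables cannot be programmed from it alone, and a programmer would have to return to 3.4.3. This is a good reason to call the problem a drafting inconsistency rather than a changed analysis, and to rate it as minor. It does not remove the conflict, because the footnote is a stated rule that would be printed under the primary safety tables.

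A second reply is that the Table B.14.3.1.1 footnote says after the last dose, not after its date. By clock time, a finding made at the Day 169 visit after the morning dose could then be post last dose. But 3.4.3 and the listing note both work by date, and the Part B AE listing shells show onset dates without times. An event that began earlier on that day, before the dose, is unclassified on either reading.

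A reader might also infer that everything found at Day 169 is lost. The documents do not support that. The window turns on onset date, not detection date, so an event discovered at Day 169 with an earlier onset is counted. Out-of-range laboratory values become AEs only when clinically significant (Protocol 12.3 and 12.7). Laboratory, liver-injury, vital-sign and examination results from that visit are summarised and listed separately whatever their AE status (Part B SAP 5.5.2, 5.5.3 and 5.5.5).

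**Conclusion.** The footnotes of Tables B.14.3.1.1 to B.14.3.1.7 and the TEAE listing shells are wrong as written; the severity is minor. They contradict SAP 3.4.3 and the Post Last Dose column in the same tables, and they leave it unclear whether Overall includes events after the last dose. The gap is one onset day per patient, the last-dose date, and for a patient with a single dosing day it is the whole TEAE window. This rests on reading the windows by date, as 3.4.3 and the listing note do.

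The number of events affected cannot be computed from the documents. It would be tempting to assume a rate of events on that day and turn it into a patient count, or to suppose that most of Table B.14.3.1.7 would go missing. Nothing in the documents gives such a rate or shows how often the event that ends treatment begins on the last-dose day. An event that begins and leads to stopping after one or more further dosing days has its onset before the last-dose date and is counted.

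**What to change.** In all Part B AE tables and TEAE listings, replace the TEAE footnote with the 3.4.3 definition: onset on or after first dose. Add one sentence stating that dose-level columns run through the last-dose date inclusive, that Post Last Dose covers onset after that date, and that Overall includes both. In Table B.14.3.1.1, word the post-last-dose footnote by date so that it matches 3.4.3 and the listing note.

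The cost is text in the shells. No new data are needed. If programs have already been written, the one check required is which end-point they use.
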